7. SAFETY ASSESSMENTS

7.1 Specification of Safety Parameters

Although we will be unable to determine if there are hospitalizations or ED visits for opioid withdrawal in patients of clinicians in the intervention group, we will monitor this potential safety issue by comparing clinicians who received a letter to controls to determine if there are any dramatic reductions (>20% from baseline) in opioid prescribing in the post-intervention period as a result of the letter. The U.S. does not have an integrated healthcare system with complete data on hospitalizations for all patients to evaluate induced withdrawal. However, it is possible for us to evaluate if providers induce withdrawal in patients by exhibiting high rates of MME reductions.

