7.3. Adverse Events and Serious Adverse Events

At any time, clinicians can report an adverse event or unanticipated problem potentially related to the letters to the medical examiner's office or the County or City public health officer who co-signs the letter and provides contact information.

We do not expect there to be adverse events directly influenced by the clinical guidance being delivered in this study. All study interventions encourage clinicians to follow well-established national guideline recommendations and known best practices. While the expectedness of adverse events is very low, we will investigate each and every numerator case identified in all safety measures described above. For cases identified by the safety monitoring measures, we will perform manual physician chart review to examine the clinical circumstances and to make a judgment (1) the expectedness of the event [unexpected, expected], (2) the likelihood that the safety event was study related [not related/possibly related/definitely related] and (3) judge the event's severity [abnormal clinical finding without symptoms/symptoms requiring clinical

intervention/short term disability or hospitalization/death AND separately define the severity as mild, moderate, or severe].

These will be conducted only by authorized study personnel. Study personnel will interview clinicians treating patients when needed to obtain additional information. Each case identified will have a case report form with these variables and will be signed and dated by study staff completing the form. These forms will be stored in a locked office. Each adverse event will be given an identification number. If study personnel believe that a patient that experienced an adverse event would benefit from seeing or communicating with their clinician who previously received a letter, the PI will within 2 business days reach out to this clinician advising them to contact the patient as soon as possible.

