7.6 Safety Monitoring

Although we will be unable to determine if there are hospitalizations or ED visits for opioid withdrawal in patients of clinicians in the intervention group, we will monitor this potential safety issue by comparing clinicians who received a letter to controls to determine if there are any dramatic reductions (>20% from baseline) in opioid prescribing in the post-intervention period as a result of the letter. The U.S. does not have an integrated healthcare system with complete data on hospitalizations for all patients to evaluate induced withdrawal. However, it is possible for us to evaluate if providers induce withdrawal on patients by exhibiting high rates of MME reductions.

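### The one quantified safety measure, a fall of more than 20% in clinicians' prescribing, cannot show abrupt loss of supply in individual patients and defines no patient cases for the review in section 7.3

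*Combined protocol and SAP*

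**What the plan says.** Section 7.1 of the combined protocol and SAP starts from a limit: the team will be "unable to determine if there are hospitalizations or ED visits for opioid withdrawal". As a substitute it proposes "comparing clinicians who received a letter to controls" and looking for "any dramatic reductions (>20% from baseline) in opioid prescribing in the post-intervention period". It then states that "it is possible for us to evaluate if providers induce withdrawal in patients by exhibiting high rates of MME reductions". No rate, denominator, window or cut-off is attached to that last phrase. Section 7.6 repeats the text almost unchanged and adds no measure. Section 7.2 says only that safety is assessed during the intervention and follow-up periods.

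Section 7.3 opens a second route, in which "clinicians can report an adverse event or unanticipated problem potentially related to the letters" at any time. It then promises that "we will investigate each and every numerator case identified in all safety measures described above". The method is manual chart review, with each case judged for expectedness, relatedness and severity. Section 7.4 adds that a patient death found through the safety measures goes to the IRB within 24 hours.

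Section 10.1 describes the data as CURES dispensing records for each provider in the sample, with patient and clinician identifiers removed before the analysis file is released.

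**The concern.** The harm and the measure sit at different levels. Withdrawal happens to a patient, whereas the measure describes a clinician or a group of clinicians. The protocol itself treats the speed of reduction as important: section 2.1 and the letter content in section 5.1 both favour slow dose reduction. A fall in prescribing carries no information about speed or about who was reduced.

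Two things are at stake. First, a finding of no fall beyond 20% would be offered as evidence on induced withdrawal, because section 7.1 says that this can be evaluated, yet the measure cannot carry that conclusion. Second, the review in section 7.3 and the death reporting in section 7.4 are written as if the measure produces patient cases, and none is defined.

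**Working it through.** **Inputs from the documents.** The 20% figure and the comparison by clinician (7.1, 7.6); fewer new starts as a secondary hypothesis (9.4.2); case review (7.3); death reporting (7.4); data source and de-identification (10.1).

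**Assumed here, because the documents give no patient-panel data.** Patients per clinician n = 10, 20 or 50. Stopped patients are on r = 1, 2 or 4 times the dose of the others. Stopped patients have no fills in the whole window, and all other patients are unchanged.

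**The plan's own figure.** The 20% is a definition with no calculation behind it, so there is nothing to reproduce. The computed 65 decedents per arm in section 9.2 does not bear on this point.

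1. *Unit and window.* Section 7.1 does not say whether the 20% applies to an arm or to each clinician; both sum over patients. It also does not say which post-intervention period is meant. Section 9.5 uses 3 months either side of the letter with a one-month washout, the Précis uses 12 months either side, and section 6.1.3 uses 13 months of follow-up.

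2. *Equal doses.* The fall in the total equals the share of patients stopped. The largest number that can be stopped without exceeding 20% is floor(0.20 × n): 2 of 10, 4 of 20, 10 of 50.

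3. *Unequal doses.* If a share p is stopped, the fall is p·r / (p·r + 1 − p).
   - r = 2, p = 0.10: 0.20 / 1.10 = 18.2%, not flagged.
   - r = 4, p = 0.05: 0.20 / 1.15 = 17.4%, not flagged.
   - Setting the fall to 0.20 gives p = 0.20 / (0.8r + 0.20), that is 20% (r = 1), 11.1% (r = 2) and 5.9% (r = 4).

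   New starts or increases elsewhere would raise these shares. So would stops partway through the window.

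4. *Same reading, different pattern.* Take 100 equal-dose patients. If all are reduced by 10%, the total falls 10% and no patient falls by more than 20%. If 10 are stopped and 90 are unchanged, the total also falls 10 / 100 = 10%, but ten patients have no supply. The measure returns the same value for both.

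5. *The other direction.* If new starts supply a share s of MME and fall by a fraction f, the total falls by s × f with no continuing patient affected. Where s × f exceeds 0.20, the safety line is crossed by an effect that the trial hopes to see.

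6. *Per-clinician reading.* Suppose a clinician's log ratio of post to baseline prescribing is normal with mean 0 (no true change) and an assumed SD σ. Then P(fall > 20%) = Φ(ln 0.8 / σ), with ln 0.8 = −0.223. This gives 13% for σ = 0.2, 23% for 0.3, 33% for 0.5 and 39% for 0.8. Such a rule could flag many clinicians by chance, and each flag would name a clinician, not a patient event.

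7. *Section 7.1 against 7.3 and 7.4.* Chart review with severity grading needs an identified patient and an event, and the death report needs a patient. A change in prescribing supplies neither. Section 10.1 removes identifiers before analysis, and the documents describe neither a step back from a flagged record to a patient nor access to charts.

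**The case against.** Several objections have force.

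- *There are other safety inputs.* This stands. Voluntary reports under section 7.3 can produce patient cases. A reader might infer that the trial has no route to any adverse-event case, and the documents do not support that.
- *The unit is open, and a rate of reductions could mean a count over patients.* The documents do not fix an arm-level reading, and a per-clinician rule would give clinicians whose charts could be examined or who could be interviewed. The claim is therefore limited to the absence of a defined patient case. The phrase about high rates of reduction is attached to providers and has no definition, so it cannot fill the gap.
- *The proxy is disclosed.* Sections 7.1 and 7.6 admit that hospital events cannot be seen. They then go further and say that induced withdrawal can be evaluated, and that is the statement at issue.
- *The patient mixes are invented.* They are assumptions and are labelled as such. Step 4 shows the lack of discrimination, and it does not depend on any particular panel size.

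A reader might also infer that the 5% difference used for sample size in section 9.2 could consist entirely of 1 patient in 20 losing all supply. The documents do not show this. Section 9.5 models log MME with no-fill days as censored and a random intercept for prescriber, and a 5% fall in a total does not translate directly into a 5% effect on that scale.

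Nor does the 20% carry over to single patients. A figure set for clinicians' prescribing has a different clinical meaning for one person. Patients whose short course simply ended would also appear as having no further fill if the tabulation were not restricted.

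**Conclusion.** The point holds in this form. Apart from voluntary reports, the only quantified safety measure is a clinician-level or arm-level fall of more than 20%, with no stated unit, window or patient-level numerator. It cannot distinguish gradual tapers from abrupt loss of supply, and it responds to fewer new starts, which are intended. Under equal doses and no other change, up to 20% of a clinician's patients could fall to zero unflagged. The share is 11.1% or 5.9% if those patients were on two or four times the others' dose. These sizes are illustrations under stated assumptions, not estimates for this trial.

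This is more than missing detail: carried out as written, the measure cannot support the claim to evaluate induced withdrawal, and section 7.3 receives no defined patient cases from it. The primary efficacy analysis is unaffected. The limit lies in the chosen measure and not in the data source, since the new-start outcome already requires fills to be linked by patient.

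**What to change.** Add a patient-level tabulation by arm from the linked CURES fills. Restrict it to patients on ongoing opioid therapy at baseline from a randomised prescriber, with ongoing therapy defined by the study team. Report the distribution of change in dispensed MME and the proportion with no further fills, over a stated window. Base any statement about induced withdrawal on that comparison between arms and not on clinician totals.

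Reconcile sections 7.1 and 7.6 with 7.3 and 7.4 on what a numerator case is. The study team sets any cut-off and decides which cases go to chart review; none is proposed here. State how a flagged patient is re-identified, which could be done at the medical examiner's office where the identifiable extract is held, and how charts are obtained.

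The cost is protocol wording and one small extra tabulation, plus whatever chart review the team chooses. There are two limits. Intended tapers are counted too, so the information lies in the difference between arms and not in either arm's proportion. Fills from non-study prescribers are missed unless the extract is widened to all fills of these patients; if it is not, a patient who moved to another prescriber would look stopped, and this should be stated as a limitation.

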7.2 Methods and Timing for Assessing, Recording, and Analyzing Safety Parameters

We will assess safety throughout the course of the intervention period and follow-up period.

7.3. Adverse Events and Serious Adverse Events

At any time, clinicians can report an adverse event or unanticipated problem potentially related to the letters to the medical examiner's office or the County or City public health officer who co-signs the letter and provides contact information.

We do not expect there to be adverse events directly influenced by the clinical guidance being delivered in this study. All study interventions encourage clinicians to follow well-established national guideline recommendations and known best practices. While the expectedness of adverse events is very low, we will investigate each and every numerator case identified in all safety measures described above. For cases identified by the safety monitoring measures, we will perform manual physician chart review to examine the clinical circumstances and to make a judgment (1) the expectedness of the event [unexpected, expected], (2) the likelihood that the safety event was study related [not related/possibly related/definitely related] and (3) judge the event's severity [abnormal clinical finding without symptoms/symptoms requiring clinical

intervention/short term disability or hospitalization/death AND separately define the severity as mild, moderate, or severe].

These will be conducted only by authorized study personnel. Study personnel will interview clinicians treating patients when needed to obtain additional information. Each case identified will have a case report form with these variables and will be signed and dated by study staff completing the form. These forms will be stored in a locked office. Each adverse event will be given an identification number. If study personnel believe that a patient that experienced an adverse event would benefit from seeing or communicating with their clinician who previously received a letter, the PI will within 2 business days reach out to this clinician advising them to contact the patient as soon as possible.

7.4 Reporting Procedures

The seriousness of the adverse event will be documented on the case report form. We will categorize all of the following as serious adverse events: patient death, life-threatening event, hospitalization-initial or prolonged, disability/incapacity, and events that required intervention to prevent permanent impairment. The clinician reviewing the event will determine the seriousness of the event. If it is an event other than those listed above that the reviewing clinician feels is an ‘other’ serious event, it will be discussed with another clinical study team member to reach consensus. All details will be documented on a case report form.

We will within a business day report any clinician reported adverse events, safety analysis, or unanticipated problems to the USC IRB. Our report will include appropriate identifying information for the study, a detailed description of the adverse event, and a description of any changes to the protocol or other corrective actions that have been taken or are proposed. If an adverse event occurs, we will review relevant clinical decision support and ensure others are not at a greater risk of harm than was previously known or recognized. Clinician participants are only receiving a letter informing them of a recent patient death due to opioid overdose. Additional patient deaths related to this study are not expected. However, should we identify a patient death in safety measures described above we will report the death to the USC IRB within 24 hours of our knowledge of the death.

7.5 Follow-up for Adverse Events

We will within a business day report any clinician reported adverse events, safety analysis, or unanticipated problems to the USC IRB. Our report will include appropriate identifying information for the study, a detailed description of the adverse event, and a description of any changes to the protocol or other corrective actions that have been taken or are proposed. If an adverse event occurs, we will review relevant clinical decision support and ensure others are not at a greater risk of harm than was previously known or recognized.

7.6 Safety Monitoring

Although we will be unable to determine if there are hospitalizations or ED visits for opioid withdrawal in patients of clinicians in the intervention group, we will monitor this potential safety issue by comparing clinicians who received a letter to controls to determine if there are any dramatic reductions (>20% from baseline) in opioid prescribing in the post-intervention period as a result of the letter. The U.S. does not have an integrated healthcare system with complete data on hospitalizations for all patients to evaluate induced withdrawal. However, it is possible for us to evaluate if providers induce withdrawal on patients by exhibiting high rates of MME reductions.

8. INTERVENTION DISCONTINUATION

It is not possible to discontinue intervention because prescribers will receive one instance of the informative communication. In the secondary research design, prescribers will receive a follow up communication if the researchers find another case where an affiliated patient has deceased.

9. STATISTICAL CONSIDERATIONS

9.1 General Design Issues

The study is a decedent-cluster randomized field experiment; clusters of prescribers within each decedent were randomly allocated to either treatment or control. This design avoided treatment contamination—clinicians prescribing to the same patient were able to share information about the intervention without diluting its effect. If two or more decedents had the same prescriber, that prescriber was assigned to one and only one of those decedents by random draw. Two factors served as random strata: 1) whether the decedent received a prescription from a clinician with a single or multiple deaths, and 2) whether opioids only, opioids in combination with benzodiazepines, or benzodiazepines only were the cause of death. The first strata is designed to form equivalent groups on prescriber risk posture. The second strata equated preference for type of scheduled drug prescribed in practice. Strata were crossed to form $2 \times 3 = 6$ randomization groups.

9.2 Sample Size and Randomization

We calculated the sample size needed to detect an effect of the letter intervention using standard formulas for power analysis in cluster randomized trials and the ‘clusterPower’ package in R statistical computing language.(19) For this calculation we used data on decedents and prescribers at the San Diego County Medical Examiner between January 1 and December 31, 2013 published in Lev et al. 2016.(20) We assume a two-tailed test with a 5% Type I error rate

and an 80% chance to detect an effect. Lev et al.(20) found mean of 4.5 prescribers for each decedent in San Diego County. Coefficient of variation was not reported by Lev et al. 2016. We assume it to be 1.22, which implies that 99% of decedents had 20 or fewer prescribers in the year before their death. We assume a 5% difference in means and a standard deviation of +140 daily MME within cluster. Most clinician clusters for process measures have intracluster correlations that fall between 0.05 and 0.15.(21) We assume a more conservative intracluster correlation of 0.2; in our design we randomized by decedent to reduce intracluster correlation. We utilized the Taylor method for calculating variance inflation due to unequal cluster sizes. Under these assumptions, we would need 65 decedents per study arm.

9.2.1 Treatment Assignment Procedures.

The study is a decedent-cluster randomized field experiment; clusters of prescribers within each decedent were randomly allocated to either treatment or control. This design avoided treatment contamination—clinicians prescribing to the same patient were able to share information about the intervention without diluting its effect. If two or more decedents had the same prescriber, that prescriber was assigned to one and only one of those decedents by random draw. Two factors serve as random strata: 1) whether the decedent received a prescription from a clinician with a single or multiple deaths, and 2) whether opioids only, opioids in combination with benzodiazepines, or benzodiazepines only were the cause of death. The first strata is designed to form equivalent groups on prescriber risk posture. The second strata equated preference for type of scheduled drug prescribed in practice. Strata were crossed to form $2 \times 3 = 6$ randomization groups.

For randomization, six decedent lists were generated from the crossed strata levels. Using random.org's sequence generator, true random integer sequences derived from atmospheric noise determined decedent order in each list. For each ordered list, prescribers to decedents in the first half were those who received the intervention.

9.3 Interim analyses and Stopping Rules

Not applicable

9.4 Outcomes

9.4.1 Primary outcome

Our primary analysis assesses changes over time before and after the intervention in natural log-transformed MME between treatment and control.

9.4.2 Secondary outcomes

As secondary hypotheses, we evaluate if the intervention cohort had 1) fewer high-dose opioid prescriptions (≥ 50 or > 90 MME per day), or 2) fewer new patients who were started on opioids. High-dose prescriptions were evaluated using censored regression on percent of clinician fills on high-dose. Chance of a fill being a “new start” were evaluated using logistic regression. These analyses were also conducted within a difference-in-differences framework.

9.5 Data Analyses

Descriptive and inferential statistics will be carried out in STATA (Version 14.0; Stata Corporation, College Station, TX). The *cmp* command in STATA will be used to compute a difference-in-differences estimator within a mixed-model censored linear regression.(17) The difference-in-differences estimator compares the average change over time in MME dispensed for prescribers in the intervention group, compared to the average change over time for prescribers in the control group. The natural log transformation of MME ensures normally distributed data. Censored regression has a continuous component and a discrete one. Natural log MME doses estimated over days where opioids were dispensed in the name of a prescriber represent the continuous part, and days with no opioids filled in that prescriber’s name represent the discrete part of the model. We denote estimation of the dependent variable as $\log(\overline{MME})^*$ to distinguish it from uncensored estimation. The analysis is represented by:

$$\log(\overline{MME})^*_{ijk} = \beta_1 x_{1ij} + \beta_2 x_{2ij} + \beta_3 x_{3ij} + \delta_{i(k)} \quad [1]$$

where β_1, β_2 and β_3 are fixed effects coefficients on time, x_1 , intervention, x_2 , and time by intervention interaction, x_3 , respectively. Alphabetic subscripts describe the i th prescriber, j th prescription filled and k th decedent, the nested random intercept $\delta_{i(k)}$ is normally distributed with mean zero and variance, $\sigma_{i(k)}^2$, for each i prescriber nested in (i.e., having prescribed to) decedent $k, i(k)$. With natural log transformed data, the value $100 \cdot [\exp\{\beta_3\} - 1]$ measures the percentage change in MME attributable to the intervention when data are uncensored.(18) However, when data are censored the coefficient β_3 must be adjusted to reflect the effect on the observed outcome. We will evaluate data 3 months pre-intervention and 3 months post-intervention, with

post-intervention beginning one month after the letter was sent to washout contamination by prescriptions written before receipt of the letter but filled afterwards. For the one-year analysis we will include a regressor to control for the 3-month effect. We will perform sensitivity analysis on regression assumptions. As secondary hypotheses, we evaluate if the intervention cohort had 1) fewer high-dose opioid prescriptions (≥ 50 or > 90 MME per day), or 2) fewer new patients who were started on opioids. High-dose prescriptions will be evaluated using censored regression on percent of clinician fills on high-dose. Chance of a fill being a “new start” will be evaluated using logistic regression. These analyses will also be conducted within a difference-in-differences framework.

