6.1.2 Enrollment, Baseline, and/or Randomization

Enrollment

Participants will not be enrolled; we will intervene on all clinicians and allied health professionals with prescribing privileges and at least one prescription drug death as part of a public health program to encourage safe prescribing in San Diego County. Informed consent of patients and clinicians is waived under HHS regulations at 45 CFR 46.116(c), as the study is evaluating a County public service safe prescribing program.

Baseline Assessments

For the baseline assessment, the study team will evaluate physician prescribing practices in the 12 months pre- intervention using data from the CURES database.

Randomization

For randomization, six decedent lists were generated from the crossed strata levels. Using random.org's sequence generator,(16) true random integer sequences derived from atmospheric noise determined decedent order in each list. For each ordered list, prescribers to decedents in the first half were those who received the intervention.

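### The primary difference-in-differences model leaves baseline MME unadjusted in a randomised trial; this costs some precision, by an amount the plan does not let one fix, but causes no bias

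*Combined protocol and SAP*

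**What the plan says.** Section 9.4.1 makes the primary outcome the change in log MME before and after the letter, compared between arms. Section 9.5 will "compute a difference-in-differences estimator within a mixed-model censored linear regression". The fixed effects in equation [1] are time (beta1), arm (beta2) and time by arm (beta3), and beta3 carries the effect. The only random term is a prescriber intercept nested in decedent. Neither baseline MME nor the randomisation strata are covariates.

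Sections 9.1 and 9.2.1 describe random allocation of decedent clusters within six strata. Section 3 names the prescriber as the unit instead, but allocation is random on either description.

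On baseline data, section 6.1.2 plans to "evaluate physician prescribing practices in the 12 months pre- intervention", and section 10.1 obtains CURES dispensing records for every provider in the sample. For the analysis, section 9.5 states: "We will evaluate data 3 months pre-intervention and 3 months post-intervention". The Précis describes a main analysis of 12 months against 12 months.

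The sample size in section 9.2 is built on a comparison of means and mentions no pre-post correlation: "We assume a two-tailed test with a 5% Type I error rate" "and an 80% chance to detect an effect".

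**The concern.** Difference-in-differences earns its place when groups may differ systematically before treatment. Under randomisation the expected baseline means are equal. Estimating beta2 freely and subtracting it removes a difference whose true value is zero, and the sampling noise of the pre-period then passes into the effect estimate. Regression on the baseline value removes only as much of the baseline as predicts the outcome.

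The difference matters because the target is small, 5% in section 9.2, and section 4.3 fixes the deaths to those catalogued from 1 July 2015 to 30 June 2016. Precision lost in the analysis cannot be recovered by further recruitment. Section 9.5 gives no reason for preferring the change contrast.

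**Working it through.** **1. The plan's own figure.** Section 9.2 arrives at 65 decedents per arm. Its inputs are 5% two-sided alpha, 80% power, an ICC of 0.2, and these: "found mean of 4.5 prescribers for each decedent in San Diego County"; for the coefficient of variation, "We assume it to be 1.22"; and "We assume a 5% difference in means and a standard deviation of +140 daily MME within cluster". The figure cannot be reproduced, because the mean to which the 5% applies is not stated. Working backwards:

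- L = 4.5 × 0.2 / (4.5 × 0.2 + 0.8) = 0.529.
- Taylor inflation = [1 + 3.5 × 0.2] / [1 − 1.22² × 0.529 × 0.471] = 2.70.
- Detectable difference with 65 per arm, taking 140 as the total SD = 2.80 × 140 × √(2 × 2.70 / (65 × 4.5)) = 53.3 MME.
- Implied mean = 53.3 / 0.05 = about 1,066 daily MME.

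This does not show that 65 is wrong. It does mean that section 9.2 cannot anchor the power of either estimator.

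**2. Relative variance.** Take pre and post prescriber means with equal variance (set to 1) and correlation rho, in a linear model.

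- Difference-in-differences: variance proportional to 2(1 − rho).
- Baseline-adjusted: variance proportional to 1 − rho².
- Ratio: (1 − rho²) / [2(1 − rho)] = (1 + rho)/2, which is below 1 for every rho below 1.

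The next table assumes values of rho, since the documents give none. Power is Phi(2.80/√ratio − 1.96), on the convention that difference-in-differences has exactly 80%.

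| rho (assumed) | Ratio | Variance saving | Power after adjustment | Decedents per arm matching 65 |
|---|---|---|---|---|
| 0.5 | 0.75 | 25% | 90% | 49 |
| 0.7 | 0.85 | 15% | 86% | 56 |
| 0.9 | 0.95 | 5% | 82% | 62 |
| 0.96 | 0.98 | 2% | 81% | 64 |

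**3. Check by simulation.** An uncensored simulation used 130 decedent clusters, ICC 0.2 and unequal cluster sizes. The ratios were 0.63, 0.78, 0.82 and 0.95 at rho 0.3, 0.5, 0.7 and 0.9, against 0.65, 0.75, 0.85 and 0.95 from the formula. On balanced data the random-intercept model's interaction coefficient equalled the simple change-score contrast to six decimals, so the random intercept recovers none of the lost precision.

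**4. Where rho might lie.** If a random intercept were the whole covariance structure, then rho = ICC / [ICC + (1 − ICC)/n], where ICC is the within-prescriber correlation of daily records and n the days per period. Both inputs are assumptions.

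- ICC 0.2, n = 90: rho = 0.96, a saving of about 2%.
- ICC 0.05, n = 20: rho = 0.51, a saving of about 24%.

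**5. Dropping beta2 alone.** Without beta2, equation [1] subtracts w times the baseline, where w is the correlation the model implies rather than the true one. The variance is 1 − 2w·rho + w². With w = 0.96:

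| True rho | Difference-in-differences | beta2 dropped | Covariate adjustment |
|---|---|---|---|
| 0.5 | 1.00 | 0.96 | 0.75 |
| 0.7 | 0.600 | 0.578 | 0.510 |

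With many daily records per prescriber, w is pushed towards 1 and most of the gain is missed.

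**6. Earlier baseline months.** Assume the correlation between quarters is 0.9 × 0.9^lag, with the one-month washout, so the last pre-quarter and the post-quarter are 4/3 quarters apart and rho = 0.78. The variances are 0.436 for difference-in-differences, 0.388 with one baseline quarter as covariate, 0.373 with four quarters as covariates, and 0.473 for difference-in-differences on a plain 12-month average. Under this assumption the longer history helps as covariates (0.373/0.436, a 14% saving) and hurts as a longer averaged pre-period.

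**The case against.** The strongest reply is that this is a matter of preference. Difference-in-differences is prespecified, is unbiased under randomisation and matches the outcome as section 9.4.1 words it. The same prescribers are observed in windows about a month apart, so rho may be high and the saving slight. The formula assumes a linear model with equal variances, whereas the plan uses censored regression. Section 9.5 also promises sensitivity analysis of regression assumptions, where an adjusted model could sit.

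Most of this stands as a limit on size. It does not remove the point: the direction is the same for every rho below 1, and a general promise of sensitivity analysis does not specify an adjusted primary estimate.

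Two objections to the remedy also stand. Dropping beta2 does not deliver the gain (step 5). And log MME is undefined for a prescriber with no opioid fills in the pre-period. Such prescribers are plausible: one stratum is benzodiazepine-only deaths, and the opioid-prescription criterion in section 4.1 carries no date window.

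A reader might infer three stronger things, none of which the documents support:

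- **That the primary result is biased.** Randomisation protects against this. Chance baseline imbalance with regression to the mean affects an individual realised estimate, not its expectation.
- **That the trial is underpowered, or that its power would rise from 80% to 90%.** The 80% starting point in step 2 is a convention. If section 9.2 is read as 80% power for a post-only comparison, difference-in-differences has about 80% at rho 0.5 and 95% at rho 0.7, and adjustment about 90% and 97.5%. The number of eligible decedents is not given either.
- **That the extra baseline months are already in hand.** Sections 6.1.2 and 10.1 describe evaluation and extraction as planned.

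**Conclusion.** The point holds as one of efficiency. The primary estimator spends precision on a baseline arm difference that randomisation sets to zero in expectation, while the plan obtains the baseline values needed to avoid this. In large samples baseline adjustment is never less precise.

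The likely saving in variance runs from about 25% (rho 0.5) down to about 2% (rho 0.96). It rests on an assumed rho, equal variances before and after, and a linear approximation to the censored model. At the low end the change hardly matters. It is still worth making because it is cheap and the number of decedents cannot be increased. It is not a validity defect.

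**What to change.** In section 9.5, make the primary estimate a censored mixed model of post-period log MME with these terms:

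- arm;
- prescriber baseline log MME, plus an indicator for no opioid fills in the pre-period, with the value assigned to the covariate in that case stated;
- the randomisation strata;
- the prescriber random intercept, as now.

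The earlier pre-intervention months may be added as a further covariate. The arm coefficient takes the place of beta3 and needs the same conversion to the observed scale that section 9.5 already calls for. Keep difference-in-differences as a sensitivity analysis.

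Do not simply delete beta2 from equation [1]. If a constrained-baseline longitudinal model is preferred, add a prescriber-by-period random effect, so that the model can estimate the pre-post correlation instead of imposing one near 1.

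The Précis and section 9.5 must first agree on whether the main window is 3 or 12 months, since this defines the baseline covariate. The change should be fixed before outcomes are compared by arm.

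The cost is one altered model specification, a new label for the primary estimator and a written rule for zero baselines. It needs no data beyond those the plan already intends to extract.
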